6.6 Visit Windows

- Visit 2 must be within 35 days of Visit 1.
- Visits 3, 6, and 9 (CMC visits) timing is determined according to midcycle timing according to calculations and/or OPK testing results rather than visit windows.
- Visits 4, 7, and 10 (PCT visits) must be between 2 and 3 hours after intercourse, with intercourse timing determined by the findings at the preceding CMC visit.
- Visits 5 and 8 (24 hour assessments after the baseline and product PCT visit) must be within 4 hours either side of that scheduled 24 hour follow up time.

7 DATA ANALYSIS METHODS

7.1 Data Management

Data Management will be overseen by [name] of BUSM (Lead Data Manager), via a 21CFR11 compliant electronic database (StudyTRAX®; ScienceTRAX, Macon, GA) with direct data entry via secure web portal. Database construction and validation will be performed in coordination with the Biostatistics and Epidemiology Data Analytics Center (BEDAC) at Boston University School of Public Health. Data analysis will be performed by [name], Professor of Biostatistics at the Boston University School of Public Health.

7.2 Sample Size Determination

To assess the primary endpoint (number of progressively motile sperm in aspirated endocervical mucus 2-3 hours after sexual intercourse), fifteen couples are planned to complete both the baseline and the product PCT visits. We calculate that this sample size will provide a power of 90% to detect a clinically significant (10-fold) reduction of progressively motile sperm per high power field, from a mean of 17 in baseline no-product cycles (Archer *et al.*, 1995; Mauck *et al.*, 1997; Mauck *et al.*, 2004; Burke *et al.*, 2010; Mauck *et al.*, 2017) to <1.7 progressively motile sperm per high power field (PMS/HPF) using study product.

7.3 Subject Populations for Analysis

Data from all women who complete both the baseline and the product PCT visits will be analyzed in the effectiveness analysis, thus including all women exposed to product. Data from all participants who receive the study product will likewise be included in the safety analysis.

7.4 Interim Analysis

No interim analyses are currently planned.

7.5 Statistical Analysis

Participants will be considered evaluable if they complete both the baseline and product PCT visits. If necessary, we will seek to recruit additional participants to achieve a total of 15 evaluable participants.

7.5.1 Primary Endpoint:

The endpoint for the primary objective (surrogate for contraceptive efficacy) will be the average number of PMS (across 9 HPF) in aspirated endocervical mucus 2-3 hours after sexual intercourse without study product versus with study product. A 10-fold or greater reduction in PMS from baseline will be considered indicative of likely contraceptive effect based on prior experience with detergent spermicides and with cervical barrier devices (Mauck *et al.*, 1997b; Mauck *et al.*, 1997c; Mauck *et al.*, 2004; Amaral *et al.*, 2004; Archer *et al.*, 1995; Mauck *et al.*, 1995;

al., 1996; Archer *et al.*, 1997; Schwartz *et al.*, 2008; Mauck *et al.*, 2017). Therefore, the main comparison of interest for the primary endpoint will be baseline [2-3 hours after intercourse without product use (Visit 4)] vs. post study product [2-3 hours after intercourse with product use (Visit 7)]. For comparison of the two time points, the Wilcoxon Signed Rank Test will be utilized.

An additional categorical analysis will compare the proportion of women with an average (also across 9 HPF) of fewer than 5 PMS/HPF, calculated separately for each test cycle to the proportion of women with \geq 5 PMS/HPF at baseline [2-3 hours after intercourse without product use (Visit 4)] vs. post study product [2-3 hours after intercourse with product use (Visit 7)]. For this analysis, the McNemar's test will be used.

7.5.2 Secondary Endpoint:

The secondary endpoint will be the incidence of Grade 2 or greater adverse events in the participant and her male partner in the interval between the baseline intercourse without product (Visit 4) and Visit 6, in comparison to the incidence of Grade 2 or greater adverse events in the interval between intercourse with product use (Visit 7) and Visit 9. Additional related analyses will include the incidence of *total* adverse events in the participant and her male partner in the interval between the baseline intercourse without product (Visit 4) and Visit 6, in comparison to the incidence of *total* adverse events in the participant and her male partner in the interval between the baseline intercourse without product (Visit 4) and Visit 6, in comparison to the incidence *total* adverse events in the interval between intercourse with product use (Visit 7) and Visit 9, as well as comparisons of adverse event severity in the two intervals. For comparison of the two intervals, the Wilcoxon Signed Rank Test will be utilized. An assessment of relatedness to study product will be made for adverse events as supplemental information. Adverse event evaluations will include symptoms, epithelial defects assessed by colposcopy, and laboratory safety blood tests. Emphasis will be placed on adverse events that are urogenital, product-related and/or serious among female and male participants.

7.5.3 Exploratory Endpoints:

Exploratory endpoints will include the following:

- 1. Antisperm antibody concentrations in *vaginal fluid* measured by ELISA at baseline, at 2-3 hours and at 24 hours after intercourse with and without product use and at 1 month after product (ZB-06 film) use.
- 2. Sperm agglutination titer in *vaginal fluid* measured by endpoint dilution at baseline, and at 2-3 hours and at 24 hours after intercourse with and without product used, and at 1 month after product use.
- 3. Concentrations of antisperm antibody in *endocervical mucus* samples measured by ELISA at baseline, and at 2-3 hours and at 24 hours after intercourse with and without product use, and at 1 month after product use.
- 4. Sperm agglutination titer in *endocervical mucus* measured by endpoint dilution at baseline, and at 2-3 hours and at 24 hours after intercourse with and without product use, and at 1 month after product use.

- 5. Concentrations of antisperm antibodies in *serum*, and measured by ELISA at baseline, at 24 hours, and at 1 month after exposure to ZB-06 film.
- 6. Sperm agglutination titer in *serum* by endpoint dilution measured at baseline, and 24 hours and 1 month after exposure to ZB-06 film.
- 7. Concentrations of immune mediators in *cervicovaginal lavage* measured via multiplex assays at baseline and at 24 hours after intercourse with and without study product.
- 8. Vaginal pH at baseline and 24 hours after intercourse with vs. without study product.
- 9. Nugent Score at Visit 6 baseline and 24 hours after intercourse with study product.

The continuous variables described in the Exploratory Endpoint section will be analyzed as follows: For two time point comparisons, the Wilcoxon Signed Rank Test will be utilized; for three time point comparisons, mixed linear model analysis will be performed. If dependent variables are not normally distributed, they will be (natural) log transformed prior to mixed linear model analysis. A significant effect will be followed by Tukey-Kramer multiple comparison tests. The mixed linear model analysis accounts for missing values should some participants fail to return for the 1 month time point. Statistical significance will be assumed when p<0.05. All analyses will be performed with SAS (Version 9.4; SAS Institute Inc., Cary, NC, USA).

An equivalence test will be performed between the average number of PMS (across 9 HPF) in aspirated endocervical mucus 2-3 hours after sexual intercourse without study product at Baseline (Visit 4) versus the average number of PMS (across 9 HPF) in aspirated endocervical mucus 2-3 hours after sexual intercourse without study product one month following exposure to study product (Visit 10). The purpose of this test is to determine whether the postcoital PMS concentrations one month following product exposure are equivalent to baseline levels. The equivalence test will be performed utilizing the two one-sided t-tests (TOST) procedure.

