1 PROTOCOL SUMMARY

Protocol Title	An exploratory Phase 1 mechanism-of-action study of ZB-06, a vaginal film containing HC4-N, an anti-sperm monoclonal antibody
Protocol Number	ZB-06-01
Short Title	In vivo anti-sperm activity of ZB-06 film
Sample Size	Screen ~ 60 couples to complete 15 evaluable couples
Population	Healthy women $18 - 50$ years of age, who have normal menstrual cycles and are not at risk of pregnancy due to prior surgical sterilization, and their male partners, with whom they are in a monogamous sexual relationship
Centers	One: Eastern Virginia Medical School
Study rationale	This study is intended to make a preliminary assessment of the potential contraceptive effectiveness and safety of ZB-06 by observing its ability to reduce motile sperm access to the endocervix.
Study Design	This is an exploratory Phase 1, single center, open-label, crossover, mechanism of action study using a surrogate marker for contraceptive efficacy (the Standardized Postcoital Test, PCT) to assess the contraceptive potential of the ZB-06 film. The study will enroll up to 35 couples to reach a total of 15 fully evaluable women who have completed the baseline and the active-product post-coital visits. The expected duration of study participation for each
	participant will be approximately three months, including the screening period.
Schedule of Procedures/Evaluations	Visit 1: Screening Visit 2: Enrollment Visit 3: Cervical mucus check at midcycle Visit 4; Baseline (no product) postcoital visit Visit 5: 24-hour follow-up Visit 6: Cervical mucus check at midcycle Visit 7: Postcoital visit after intercourse using ZB-06 film Visit 8: 24-hour follow-up Visit 9: Cervical mucus check at midcycle Visit 10: No-product postcoital visit 1 month after ZB-06 film use

Study Duration	Estimated total study duration, 18 months; individual participation, three months				
Test product, dose, and mode of administration	ZB-06 film: The ZB-06 film contains 20 mg of the HC4-N sperm-agglutinating antibody which will be digitally inserted into the vagina by the participant 30 min before intercourse timed to midcycle, after documentation of sperm-receptive endocervical mucus in the preceding mucus check visit.				
Reference therapy, dose, and mode of administration	Baseline PCT cycle, conducted without use of ZB-06 film				

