4.2.4 Replacement of Subjects and or Repeat of Product Use Cycle

Approximately 15 women will complete the study. Participants who discontinue early may not re-enroll. Participants who discontinue may be replaced as needed to achieve the desired full 15 women completing both a baseline and a product PCT cycle. Participants who have a failed product use cycle, due to factors such as but not limited to: erectile dysfunction, inability to ejaculate, illness, etc., may repeat the product use cycle with a second dose of the 20 mg film, in a subsequent menstrual cycle

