Yes	Yes			✓		Barrier failed.			
Yes	No			✓		Continue to safety			
No Yes				✓	Good PCT. Continue to next cycle if	cycle. Discontinue			
No	No			✓	baseline cycle and exit participant from	was clearly due to participant misuse of the product.			
Insufficient material	Yes			✓	safety cycle				
Insufficient material	No			✓					
Yes	No	✓				Poor mucus may be			
Yes	No		✓		Poor mucus may be responsible for	responsible for scarcity			
No	No		✓		Repeat cycle	or lack of sperm in			
Insufficient material	No		✓			cervix. Repeat cycle.			
No	Yes	✓							
No	No	✓			Ejaculation may not have taken place.	Ejaculation may not			
Insufficient material	Yes	✓			Repeat cycle.	Repeat cycle.			
insufficient material	No	✓							

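### Sections 7.3 and 7.5 make attendance at Visits 4 and 7 the only test of evaluability, so a Visit 7 result that Appendix B sends to a repeat cycle can be analysed and count toward the 15

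*Combined protocol and SAP*

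**What the plan says.** Section 7.5: "Participants will be considered evaluable if they complete both the baseline and product PCT visits". Section 7.3 uses the same condition: "Data from all women who complete both the baseline and the product PCT visits will be analyzed in the effectiveness analysis". It adds "thus including all women exposed to product". The synopsis plans to enrol "up to 35 couples to reach a total of 15 fully evaluable women", again defined by completing the two postcoital visits.

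Appendix B has a separate column of actions for the test cycle. Results with adequate mucus, fewer than 5 PMS in the endocervix and no doubt about ejaculation are barrier successes. Every result of 5 or more is a barrier failure, even with inadequate mucus. The remaining rows lead to a repeat, for two reasons, which read most clearly in the baseline/safety column and recur in substance in the test-cycle column: "Poor mucus may be responsible for" the scarcity of sperm, or "Ejaculation may not have taken place". The test-cycle entry for poor mucus ends "cervix. Repeat cycle".

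On whether the repeat happens, Section 4.1 is permissive, and Section 4.2.4 says that women with a failed product cycle "may repeat the product use cycle with a second dose of the 20 mg film". Section 6.5.4 ties only baseline results to Appendix B by name.

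**The concern.** The plan recognises that some low Visit 7 counts may say nothing about the film, because poor mucus or absent ejaculation could explain them. The analysis rule then ignores that distinction. A woman with a flagged Visit 7 who does not repeat has still completed both visits, so she is analysed and fills one of the 15 places. If she does repeat, she has two Visit 7 results that meet the definition.

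The exposure is lopsided. At baseline the same rows call for a repeat, and Section 6.5.4 explicitly sends baseline results to Appendix B, so flagged values are more likely to enter on the film side of the pair. What is at stake is the <5 PMS/HPF comparison, the reading against the 10-fold criterion and, to a lesser degree, the Wilcoxon test.

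**Working it through.** **1. The plan's own figure.** Section 7.2 gives n = 15, a fall from 17 to below 1.7 PMS/HPF (difference 17 − 1.7 = 15.3) and 90% power. No standard deviation or sidedness is given, so 90% cannot be reproduced. With a two-sided paired t-test at 0.05 it implies a paired-difference SD of about 17.0. At that SD, power is 88% with 14 pairs, 85% with 13 and 81% with 12, so losing flagged pairs without replacement has a cost.

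**2. Rows in Appendix B.** Eight test-cycle rows lead to a repeat. Four have inadequate mucus (one with no endocervical sperm, three with some sperm but <5 PMS). Four have no endocervical sperm and either no sperm or insufficient material in the vaginal pool. None reaches 5.

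**3. Following a flagged Visit 7 through the plan.**
- Section 6.5.3: at Visit 6 the mucus score must be at least 10 with no sperm. This check can precede Visit 7 by up to 27 hours, and Appendix B still provides for inadequate mucus in the test cycle.
- Section 6.5.4: Visit 7 is cancelled when intravaginal ejaculation is known to have failed. This cannot catch ejaculation doubted only from the Visit 7 sample.
- Sections 7.3 and 7.5: no exclusion, no reference to Appendix B, no rule for choosing between two Visit 7 results.

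**4. The <5 PMS/HPF proportion.** One case is 1/15 = 6.7 percentage points. That is a maximum, because it assumes a valid test would have given 5 or more. If a valid test would be below 5 with probability p, the expected gain is 6.7 × (1 − p); at an assumed p = 0.9 it is 0.7 points. In McNemar's test, each false value paired with a baseline of 5 or more is a discordant pair in the film's favour. Five such pairs alone give exact p = 0.063; six give 0.031.

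**5. The mean fold reduction** (baseline mean 17, so the threshold is 17/10 = 1.7; the Visit 7 values are assumed and chosen near it).
- Zeros help the film: 13 valid tests averaging 1.9 give 17/1.9 = 8.9-fold. Adding two zeros gives 1.9 × 13/15 = 1.65 and 17/1.647 = 10.3-fold.
- Values between 1.7 and 5 can hurt it: 14 valid tests averaging 1.6 give 17/1.6 = 10.6-fold. Adding one poor-mucus value of 4 gives (14 × 1.6 + 4)/15 = 1.76 and 17/1.76 = 9.7-fold.
- Inert film with k zeros: the expected ratio of means is 15/(15 − k), or 1.15 for k = 2 and 1.25 for k = 3. Reaching 10 would need 14 zeros of 15.

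**6. The Wilcoxon test, inert film.** This was simulated with 4,000 trials per setting, lognormal counts with mean 17, coefficient of variation 0.6 or 1.0 and within-woman correlation 0.5 (all assumed), counting two-sided p < 0.05 in the film's favour (nominal 2.5%).

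| Zeros among 15 | Flagged results kept | Flagged results excluded |
|---|---|---|
| 0 | 2.3–2.5% | 2.3–2.5% |
| 1 | 4.4–4.8% | 2.8–3.0% |
| 2 | 7.1–7.2% | 2.4–2.5% |
| 3 | 10.4–12.6% | 2.1% |

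**7. Couples needed.** To keep 15 usable pairs, 15/(1 − r) women must complete Visit 7. For assumed r of 10, 15, 20 and 25% this is 17, 18, 19 and 20, all below 35.

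**The case against.** The best defence is that Appendix B tells the site, without qualification, to repeat these cycles. Section 4.1 points to Appendix B for cycles in general. Section 4.2.4 speaks of failed product cycles and of replacing women who discontinue, which suggests that flagged results were never meant to stand. The Visit 6 mucus check, the cancellation of Visit 7 after known failure of ejaculation, and each couple's earlier success at baseline make such cases less likely. The explicit option to decline a second product cycle, in Section 6.5.4, concerns couples who never reach Visit 7. All of this is fair and limits how often the problem will arise. It does not supply a rule for a repeat that does not take place, or for two Visit 7 results.

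A reader might infer that the plan itself calls these results uninterpretable. It does not; it assigns them to a repeat because another explanation is possible. A reader might also infer that the error always favours the film. That holds for the <5 proportion and for zeros, but not for the 10-fold reading when a value between 1.7 and 5 is kept. Moreover, Section 6.1 bases qualitative change on the median and IQR, so an illustration with means shows only one route.

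The footnote to Appendix B raises a real difficulty for the remedy: an empty vaginal pool may reflect a hostile vaginal environment in the test cycle. Excluding on a finding made after the film is used could remove genuine effect, so the all-completers result must also be shown.

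**Conclusion.** The point holds as a gap between the stated analysis rule and the plan's own classification of Visit 7 results. Followed as written, Sections 7.3 and 7.5 admit results that Appendix B attributes to possible poor mucus or absent ejaculation, and count them toward the 15.

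The size is modest and rests on an unknown number of cases. The gain is at most 6.7 points per case in the <5 proportion, and a shift across the 10-fold threshold occurs only when the valid results already lie close to it. Under the assumed distributions, the false-positive rate for an inert film is about 7% with two zeros, against a nominal 2.5%. It would be wrong to conclude that one or two false zeros could make an inert film appear 10-fold effective. The change is worth making before data are analysed, because with 15 pairs a later decision about individual women would be hard to defend.

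**What to change.** In Sections 7.3 and 7.5:
- Define the primary effectiveness set as couples with a Visit 4 that qualifies under Appendix B and a Visit 7 that Appendix B classes as barrier successful or barrier failed. Use the mucus and vaginal-pool readings of the evaluator who, under Section 4.3, is blinded to cycle and product use.
- State that, after a repeat, the first such Visit 7 is analysed.
- State that couples without one do not count toward the 15 and are replaced within the existing cap of 35.
- Report all completers as a sensitivity analysis, because an empty vaginal pool may be a product effect.
- Reconcile the statement in 7.3 about including all exposed women with Section 6.5.4, under which a woman can use the film and never have a Visit 7.

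Whether and how a product cycle is repeated is for the sponsor to decide. Sections 4.1, 4.2.4 and 6.5.4 and Appendix B should be reconciled on it.

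The cost is a few sentences, possibly a few more couples within the cap, and perhaps a slightly less favourable headline reduction.

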At ovulation, the participant's cervical mucus will be assessed by Insler scoring. Once adequate cervical mucus is documented to be present, the couple will have unprotected intercourse within approximately 24 hours of the cervical mucus check. Two to three hours after intercourse, the participant's vaginal fluid and cervical mucus will be evaluated for the presence of sperm (motile, immotile). The expectation is that at baseline, participants will have an average of greater than 5 motile sperm per high power field (HPF), averaged over 9 HPFs, and that with the use of the ZB-06 film, participants will on average have at least a 10-fold reduction in motile sperm per HPF, averaged over 9 HPFs.

The secondary objective will be assessed at each visit, by querying participants regarding any treatment-emergent adverse events (TEAEs). TEAEs from the male sexual partner will be assessed at each visit, per the female participant's report or from the male directly. The male partner will be interviewed for TEAEs by phone within 72 hours of intercourse with product. Safety will also be assessed by comparing the concentrations of cervicovaginal (CV) mucosal cytokines and chemokines with and without ZB-06 film use.

Finally, an estimation of the *in vivo* pharmacokinetics of HC4-N will be described in serum cervical mucus, and CV fluid. Our expectation is that serum levels of ZB-06 will be very low to unquantifiable, while CV fluid levels will be high, supporting local activity of the product.

A listing of all study procedures and sampling is provided in the Schedule of Events Table in Appendix A.

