4.2.3 Withdrawal of Subjects

Participants who sign the informed consent and agree to participate in the study, but do not meet eligibility criteria prior to undergoing the initial cervical mucus check (Visit 2) will not continue in the study. No electronic case report forms (eCRFs) will be completed for participants who do not undergo the cervical mucus check at Visit 2.

Once a participant undergoes Visit 2 procedures, she may be withdrawn from the study for the following reasons:

- Inability to achieve adequate cervical mucus in two attempts at the baseline cycle
- Inadequate sperm in endocervical aspirate during baseline testing, despite adequate mucus and presence of sperm in vaginal pool
- Medical reasons, including diagnosis of an STI (in the participant or her partner) or any intercurrent illness that would jeopardize the participant's health or the interpretation of the results of the study
- Failure to follow protocol requirements that is judged severe enough by the investigator to significantly affect study outcomes
- Pregnancy
- Any AE, laboratory abnormality, or intercurrent illness which, in the opinion of the investigator, indicates that continued participation in the study is not in the best interest of the subject
- Personal reasons (participant request)
- Discontinuation of entire study

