- At visit 6, we will provide the participant with a ZB-06 film to use and instruct her to insert the film deep in to the vagina about 30 minutes prior to intercourse. A back up film may also be provided upon participant request or at the discretion of the investigator.
- A directed physical exam will be performed if indicated.
- The participant will be instructed to ask her partner, prior to her next visit, if he has had any AEs involving the urogenital system or whether he has had any serious AEs.
- 6.5.4 Visits 4, 7, 10 (PCT Baseline Cycle, PCT ZB-06 Cycle and post-product-use safety cycle

The participant will return to the clinic 2-3 hours after coitus ends and within 27 hours of the mucus check visit (above, visits 3, 6 and 9).

- The participant will be asked if she has any new or worsening medical problems or symptoms or used any medications since the last study visit. In addition, she will be asked if her partner has had any AEs involving the urogenital system or associated with the use of study products (as applicable) and whether he has had any serious AEs.
- A blood sample (approximately 2 teaspoons) will be obtained at visit 7.
- A wet mount or urine dipstick, or other tests, will be performed if indicated. If the test is positive for candidiasis, BV, or UTI the participant will be treated, preferably with oral medication, and continued in the study.
- Vaginal swabs or aspirate, and endocervical mucus will be obtained.
- The participant will again undergo a pelvic exam during which a sample of cervical and vaginal secretions will be evaluated for midcycle characteristics and the presence of sperm. At visits 4 and 7, a colposcopy exam of the cervix and vagina will be performed to observe if there are signs of irritation of the external genitalia, cervix, and vagina will be noted as observed with naked eye. Baseline PCT results will be interpreted and managed as listed in Appendix B.
- A directed physical exam will be performed if indicated.

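### If Appendix B's cut of 5 decides who enters the product cycle, the supportive Visit 4 vs Visit 7 McNemar test at that same cut has no pair that can count against the film

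*Combined protocol and SAP*

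**What the plan says.** Section 7.5.1 makes the Wilcoxon signed rank test of Visit 4 against Visit 7 the main comparison, with a 10-fold fall as the benchmark. It then adds: "An additional categorical analysis will compare the proportion of women with an average (also across 9 HPF) of fewer than 5 PMS/HPF". The sentence is hard to parse, but a paired table of below 5 against 5 or above at the two visits is the only reading that fits what follows: "For this analysis, the McNemar's test will be used". Exact, corrected or uncorrected is not stated.

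For Visit 4, section 6.5.4 says: "Baseline PCT results will be interpreted and managed as listed in Appendix B". In that table only the rows with 5 or more progressively motile sperm rate the test as good and send a baseline couple on. Low counts with poor mucus lead to a repeat. Low counts with adequate mucus and sperm in the vaginal pool carry a warning that the same result in the test cycle would look like product success, and no legible instruction to continue.

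Section 4.2.3 states that a woman past Visit 2 is one of whom "she may be withdrawn from the study for the following reasons" holds, and lists "Inadequate sperm in endocervical aspirate during baseline testing, despite adequate mucus and presence of sperm in vaginal pool". It gives no number. Appendix B gives 5 but no unit. Section 4.1 mentions more than 5 per HPF at baseline only as an expectation.

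The analysis set in section 7.3 does not mention any of this: "Data from all women who complete both the baseline and the product PCT visits will be analyzed in the effectiveness analysis".

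**The concern.** McNemar's test compares two discordant cells: women who go from 5 or above to below 5, and women who go the other way. Its null hypothesis is that the two are equally likely. If entry to the product cycle requires 5 or more at Visit 4, the second cell is empty by selection. Ordinary cycle-to-cycle variation then produces discordant pairs in one direction only, and the test counts each as evidence for the film. The p-value cannot separate a film effect from women drifting below 5 on an unprotected repeat.

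At stake is whether this result may be presented as separate support for the film. The same selection also bears on the Visit 4 vs Visit 7 Wilcoxon test and on the Visit 4 vs Visit 10 equivalence test (TOST) in section 7.5.3, since both use the selected baseline.

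**Working it through.** **Inputs.** 15 evaluable couples and a baseline mean of 17 (section 7.2: "from a mean of 17 in baseline no-product cycles"); cut of 5 (section 7.5.1); p<0.05 (section 7.5.3). No SD or within-couple correlation is given, so these are assumptions.

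**The plan's own figure.** No operating figure is given for the McNemar analysis. The 90% power in section 7.2 cannot be reproduced without an SD, but the SD it implies can be solved. For a difference of 17 − 1.7 = 15.3 and a two-sided paired t-test, an SD of differences of 17.0 gives noncentrality 15.3 × √15 / 17.0 = 3.49 and power 90%.

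**Threshold.** Let b be the number of women below 5 at Visit 7, with the reverse cell 0.
- Exact: p = 2 × 0.5^b. b = 5 gives 0.063; b = 6 gives 0.031.
- Continuity-corrected: chi-square = (b − 1)²/b. b = 5 gives 0.074; b = 6 gives 0.041.
- Uncorrected: chi-square = b. b = 3 gives 0.083; b = 4 gives 0.046.

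So 6 women suffice (exact or corrected), or 4 (uncorrected).

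**Inert-film rate.** Let q be the chance that a woman with Visit 4 at 5 or above is below 5 on an unprotected repeat. The rate is P(Bin(15, q) ≥ 6) or P(Bin(15, q) ≥ 4). It passes 5% at q = 0.191 (exact) or 0.097 (uncorrected).

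**Size under assumed data.** Lognormal counts, strict gate, 40,000 simulated trials of 15 couples per setting. The mean of 17 may describe couples before or after gating, so both are shown. Ranges run over correlation 0.7 to 0.3. The Wilcoxon column counts results in the film's favour (nominal 2.4%).

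| Mean of 17 | Log-SD | q | Exact McNemar | Uncorrected | Wilcoxon |
|---|---|---|---|---|---|
| before gating | 0.7 | 0.05–0.07 | <0.1% | 0.6–1.9% | 3.3–4.0% |
| before gating | 0.9 | 0.10–0.15 | 0.2–1.9% | 6–19% | 4.6–7.0% |
| before gating | 1.1 | 0.15–0.24 | 2–12% | 18–48% | 6–11% |
| after gating | 0.7 | 0.06–0.09 | ≤0.1% | 1.0–3.6% | 3.5–4.8% |
| after gating | 0.9 | 0.14–0.21 | 1–8% | 14–40% | 6–11% |
| after gating | 1.1 | 0.23–0.36 | 11–48% | 46–85% | 11–23% |

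At log-SD 0.5 both McNemar rates are essentially zero and the Wilcoxon is close to nominal. Across all 24 settings the Wilcoxon favoured an inert film more often than exact McNemar in 20; it is below or level with it only at log-SD 1.1. No simulated inert-film trial showed a 10-fold fall in the median.

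**If the gate is loose.** In the worst setting (log-SD 1.1, correlation 0.3), admitting a quarter or half of the couples below 5 cuts the exact rate to 13% or 4% (17 after gating), or 5% or 2% (before). If half of the low test-cycle results are repeated under Appendix B, it falls to 15–19% (after) or 1.5–2.3% (before).

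**Visit 7 vs Visit 10, inert film.** Signed-rank favours the film in 2.2–2.5% of trials and exact McNemar in at most 0.6%. Under a true 10-fold effect, 91–99% of women are below 5 at Visit 7, against 1–36% with an inert film.

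**The case against.** The strongest reply is that the gate is not established. It is read from a table whose layout is damaged, section 4.2.3 makes withdrawal discretionary and gives no number, and Appendix B prints no unit. That stands, and the point is conditional on it. A reader might infer a firm entry rule at 5 PMS/HPF; the documents do not state one.

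Second, the inflation may be nil. The implied SD of 17 corresponds, if Visit 7 varies little and 17 is the ungated mean, to a CV near 1 and a log-SD of √(ln 2) = 0.83. At correlation 0.3 to 0.7 the exact rate is then 0.1–0.7% and the uncorrected rate 3–11%. This also stands: the fault in the test's logic is certain once the gate is followed, but its size is not, and it depends heavily on the unstated McNemar version.

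Third, part of the remedy is already planned. Section 6.1 summarises each cycle and compares with no-product cycles in the plural, section 7.5.1 computes the proportion below 5 for each test cycle, and section 4.1 describes the baseline as a qualifying cycle. True, but none of these says that the Visit 4 comparison is affected by selection.

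Fourth, no decision rule uses this p-value. Correct, and this limits the severity.

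**Conclusion.** To the extent that Appendix B is followed at Visit 4, the section 7.5.1 McNemar p-value is not a valid test of film effect. This is a minor fault in a supportive analysis. Its size rests on assumed spread, correlation, gate strictness and the reading of 17: from effectively nothing at log-SD 0.7 or below with the exact test, up to 12% or 48% in the extreme setting, and up to about 48% or 85% uncorrected.

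Three stronger readings might be inferred and are not supported. The test is not bound to be significant: if no woman falls below 5 at Visit 7, p is 1. The Wilcoxon is not the safer of the two: its tilt is usually larger than that of exact McNemar, at about 2.5–11% before gating and up to 23–24% after. And the primary conclusion is not undermined, because the plan's benchmark is a 10-fold fall, which selection at 5 hardly imitates.

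**What to change.** In section 7.5.1, drop the Visit 4 vs Visit 7 McNemar p-value or label it descriptive. Report the proportion below 5 PMS/HPF at Visit 7 with an exact 95% interval (for example 6/15: 16–68%; 14/15: 68–99.8%), building on the per-cycle summaries already planned, and say that it has no concurrent control.

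Add Visit 7 vs Visit 10, by signed-rank and exact McNemar, as a sensitivity comparison for both the Wilcoxon and the categorical analysis. Visit 10 is not gated at 5: Appendix B keeps a low safety-cycle result with adequate mucus and sperm in the vaginal pool, and comments on it as possible antibody induction.

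Keep the Wilcoxon test and the 10-fold benchmark. State in sections 7.3 and 7.5 that Visit 4 is a selected baseline and that this tilts both the Wilcoxon and the TOST. Report all Visit 4 results, including couples not continued. Reconcile section 4.2.3 with Appendix B on number and unit.

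The cost is an amendment under section 9.4, with no new visits or samples. There are three downsides. Couples without Visit 10 drop out, so their Visit 7 values should be listed; if a quarter or half of the women at 5 or above at Visit 7 were lost, the inert-film signed-rank rate would be 2.1–3.8% or 1.8–6.2%. A residual or induced antibody effect would make the comparison conservative. Balance between Visits 7 and 10 also assumes that misuse failures are not repeated in the test cycle alone, and the Appendix B entry on misuse is not fully legible.
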